3.3.2 Sponsor Responsibilities

The sponsor will select only qualified investigators to participate in the research study and will provide investigators with a study protocol and the information they need to properly conduct the study. The sponsor will also assure monitoring is conducted according to the monitoring plan. IRB approval of the study must be obtained prior to start of the study and this documentation will be kept on file. The sponsor will promptly notify the IRB of any significant new information about this investigation.

3.3.3 Investigator Responsibilities

Investigators are responsible for conducting the study in accordance with the signed Investigator's Letter of Agreement, the investigational plan, any IRB imposed conditions, and applicable FDA regulations for protecting the rights, safety, and welfare of subjects under the investigator's care, and for obtaining informed consent from each research participant prior to any study-related procedures. Investigators are also responsible for maintaining control of the investigational device.

This early feasibility study is being conducted at Vanderbilt University Medical Center, Nashville, TN, USA. Investigators may determine if potential subjects would be interested in taking part in the investigation prior to IRB approval, but written informed consent will not be obtained from study participants and study participation will not be allowed until IRB approval is received.

The investigational device will only be used on research subjects with the investigator's supervision and will not be used on any person who is not authorized under 21CFR812 to receive it.

Investigator will disclose accurate financial information to allow complete and accurate certification or disclosure statements that may be required by Vanderbilt University Medical Center in compliance with the institutions policies, as appropriate, and will update these records promptly if any relevant changes occur during the course of the clinical study and for one year after the completion of this study.

3.3.4 Selection of Investigators

All clinical investigators taking part in this study are accomplished gastrointestinal endoscopists who commonly perform endoscopic procedures as part of their practice. All understand and will comply with their responsibilities regarding adherence to the approved protocol and the signed Investigator's Letter of Agreement. The research protocol will take place at Vanderbilt University Medical Center, Nashville, TN, USA with the principal investigator (PI) being [name], MD, MPH, FASGE, FACG, AGAF. His *curriculum vitae* is included in Appendix H.

3.3.5 Informed Consent

Once a potential study subject has been identified, a member of the research team will present the research study to the subject in person, via phone, or via secure electronic transfer (e.g. secure email or My Health at Vanderbilt electronic portal). The potential participant will be provided with a copy of the consent form to read and will be provided with an opportunity to ask questions. Once the study participant's questions have been answered and prior to performing any study-related procedure, an IRB-approved consent form will be signed and dated by the study

participant and by the person obtaining informed consent. A copy of the signed consent form will be provided to the subject and the informed consent process will be documented in the study participant's medical record.

3.3.6 Confidentiality

Participants will receive a 3 digits identification number from 001 to 005 in the order of their enrollment. Patient identification numbers will be linked to their name on a password secured Vanderbilt University Medical Center RedCap Database only accessible by approved research study staff. Data from the hard copies of the completed surveys and questionnaires will be entered into a RedCap form and securely stored on a Vanderbilt University Medical Center password protected cloud platform accessible only by approved research study staff. The hard copies will then be destroyed after the data has been entered into electronic format. At the conclusion of the research study, the PI will maintain the information on the RedCap secure, encrypted, Vanderbilt University Medical Center system.

PROTOCOL TITLE:

Visualization of the colon through use of the Magnetic Flexible Endoscope
(MFE) in healthy participants

NCT05833789

Protocol Version Date: December 16, 2022

Statistical Analysis Plan:

Given the small sample size of study (n=5 patients), statistical analysis will be limited to descriptive statistics with median and quartiles [Q1, Q3]; median, maximum and minimum values; as well as means and standard deviations when appropriate. Percentages of groups and event numbers will be calculated.

Primary outcome measure will be noted as number of participants as a percentage of the group as a whole (n=5, denominator).

Secondary outcome measure of tolerability will be noted as number of non-tolerability events as a percentage of the group as a whole (n=5, denominator).

Secondary outcome measure of endoscopist experience by NASA Task Load Index (TLX) will be calculated as median with Q1, Q3 for each sub-scale.

Secondary outcome measure of colon mucosal visibility will be calculated as median with interquartile range.

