3. PROTOCOL

3.1 Study Protocol

3.1.1 Protocol Overview

Investigational Device: Magnetic Flexible Endoscope

Study Title: Visualization of the colon through use of the Magnetic Flexible Endoscope in healthy participants

Study Design: Early Feasibility Study

Number of Participants: 5

Study Population: Adult healthy patients who are already scheduled for their standard of care colonoscopy screening examination.

Study Duration: Standard colonoscopy examinations for healthy individuals are relatively short duration outpatient procedures lasting on average 20 to 40 minutes in total procedure time and 90 to 180 minutes in total in-facility time. Navigation and inspection of the colon, from rectum to cecum, using the MFE will be a relatively short duration outpatient procedure lasting no more than 40 minutes in total procedure duration. As is standard of care at VUMC, a post-procedure follow-up phone call is then conducted 3-5 days post-procedure.

Schedule: (1) Screening of patients for meeting inclusion criteria; (2) Administration of pre-study survey; (3) Routine colonoscopy examination with a standard colonoscope; (4) Passage of the Magnetic Flexible Endoscope from rectum to cecum; (5) Post-study structured interview and single question survey; (6) Follow-up phone call 3-5 days post examination as per VUMC standard practice for patients who have undergone colonoscopy.

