3.0.1.1 Study Endpoints

PRIMARY

1. Cecal intubation rate (success/fail)
 - a. Successful cecal intubation will be confirmed per standard endoscopic practice of visualizing and photo documenting at least 2 of the 3 common cecal landmarks (ileocecal valve, triradiate fold, appendiceal orifice).

SECONDARY

1. Mucosal visibility
 - a. An operator assessed score, the Colon Visualization Index (Appendix A), will be used.
2. Patient tolerance
 - a. Pain perception will be assessed with a validated pain score (Wong-Baker FACES Pain Rating Scale; Appendix B). Qualitative assessment of participant sentiment will be assessed with a post-study structured interview (Appendix C).
3. Endoscopist experience
 - a. The usability of the platform in terms of task load for the endoscopist will be assessed using the standardized validated NASA Task Load Index (TLX) instrument (Appendix D).

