3.0.4.1 Day of Endoscopy

The patient will be administered the Pre-Study Survey (Appendix G) consisting of the RAND 36-Item Short Form Survey, PROMIS Scale v1.0 Gastrointestinal Belly Pain, PROMIS Scale v1.1 Gastrointestinal Gas and Bloating 13a, and PROMIS Scale v2.0 Pain Intensity 3a.

Once the patient has been successfully prepared for the colonoscopy procedure and has been administered monitored anesthesia care (MAC) by the VUMC Anesthesia team as per routine care, the following steps will be followed.

Note: only step “B)” below deviates from the current standard clinical practice for colonoscopic examination of healthy patients. Step “B)” is when the investigational Non-Significant Risk (NSR) device is used and the only step that is not usually performed during colonoscopic examinations.

- A) *Colonoscopic assessment using a standard colonoscope.* This assessment is the first step in the routine patient colonoscopy examination. During this step, the colonoscopist introduces a colonoscope into the patient to assess the rectum, colon, and cecum for polyps. This will be performed per standard of care without deviation from standard of care procedure.
- B) *Colonoscopic visualization of the cecum using the Magnetic Flexible Endoscope (MFE).* After the colonoscope assessment is complete, anesthesia is stopped, and the standard colonoscope is removed from the patient, the MFE device will be lubricated, introduced into the patient, and navigated to the cecum. Steps in sequential order are:
 1. The MFE device’s sterile packaging will be inspected and confirmed intact
 2. The MFE package will be opened
 3. The MFE will be lubricated
 4. The MFE will be inserted into the patient via the anus
 5. The MFE will be navigated to the cecum
 6. The MFE will be removed from the patient
- C) *Any adverse events occurring during the surgical procedure will be documented.* Any adverse events that occur during the procedure will be documented and reported in accordance with 21 CFR 812 and Vanderbilt’s IRB protocols.

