3.0.4.3 Participant Termination/Withdrawal

Patients may be terminated from the study for the following reasons:

- A change in patient's health status that would preclude continuation in the study (e.g. cardiac event during endoscopic procedure). If this would occur, the patient will continue to be followed as per routine care.
- If the patient changes their mind and requests to be withdrawn from study should this occur, data will continue to be collected unless the patient requests in writing for data collection to cease.

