3.1 Data Analysis

In this early feasibility study, our primary endpoint is safe, successful, cecal intubation with the MFE. Mucosal visibility, patient tolerance, and endoscopist feedback on the platform will also be captured as secondary endpoints.

We will stop enrolling patients in this study if:

1. We do not believe that additional patients should undergo the procedure because the risks of the procedure outweigh the potential benefits to participants

and/or

2. An unanticipated adverse effect would warrant that the study be stopped for assessment of the effect.

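### The SAP divides non-tolerability events by a fixed 5, which gives the share of MFE-exposed participants only if all five are exposed and none has more than one event

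*SAP*

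**What the plan says.** The SAP gives one summary for tolerability: "Secondary outcome measure of tolerability will be noted as number of non-tolerability events as a percentage of the group as a whole (n=5, denominator". The sentence just before it, on the primary outcome, uses a different numerator: "Primary outcome measure will be noted as number of participants as a percentage of the group as a whole (n=5, denominator". So the unit on top changes from participants to events while the 5 underneath stays the same.

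Protocol 3.0.1.1 measures tolerance in two ways: "Pain perception will be assessed with a validated pain score (Wong-Baker FACES Pain Rating Scale; Appendix B" and "Qualitative assessment of participant sentiment will be assessed with a post-study structured interview (Appendix C". The schedule in Protocol 3.1.1 lists a "Post-study structured interview and single question survey". The supplied text does not say which of these produces an event, and it does not limit events to one per person.

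Three places in the protocol bear on the denominator:

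- Section 3.0.4.1 puts the MFE last: "After the colonoscope assessment is complete, anesthesia is stopped, and the standard colonoscope is removed from the patient", and only then is the MFE introduced.
- Section 3.0.4.3 allows a participant to be taken out for a health change that would "preclude continuation in the study (e.g. cardiac event during endoscopic procedure", and also allows withdrawal on request. After a withdrawal, data collection goes on unless the participant asks in writing for it to end.
- Section 3.1 Data Analysis has a rule beginning "We will stop enrolling patients in this study if", so fewer than five may be enrolled.

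Neither document says what the denominator becomes in these situations, and neither gives a replacement rule.

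**The concern.** A reader will take a tolerability percentage with a base of five as the share of participants who did not tolerate the MFE. The ratio as written need not be that share, for two separate reasons.

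First, if one person can contribute more than one event, events over people overstates the share affected and can exceed 100%.

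Second, a person who never receives the MFE cannot fail to tolerate it. If five enrol and fewer are exposed, dividing by 5 counts the unexposed as having tolerated the device. If enrolment stops early, 5 is not the size of any group in the study.

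What is at stake is how one descriptive result reads. No test, sample size or decision threshold uses it.

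**Working it through.** **Inputs from the documents.** The numerator is events and the denominator is 5 (SAP). Planned enrolment is 5 (Protocol 3.1.1, 3.0.1.0 and 3.0.4.0), so the SAP's 5 matches the plan. The SAP calculates no result for tolerability, so there is no figure to reproduce.

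**Assumed inputs, for illustration.** The documents give no number of events per person and no withdrawal rate. I take at most m = 1 or 2 events per person, and k = 3, 4 or 5 participants exposed. E is the total number of events and a is the number of participants with at least one event.

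- SAP figure = E/5
- Share of exposed participants affected = a/k

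**Step 1: five exposed, at most one event each (k = 5, m = 1).** Then E = a, and E/5 takes the values 0, 20, 40, 60, 80 or 100%. Both figures agree.

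**Step 2: numerator (k = 5, m = 2).** Given E, the number affected lies between E/2 (rounded up) and the smaller of E and 5.

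| Events E | SAP figure E/5 | Participants affected | True share |
|---|---|---|---|
| 2 | 2/5 = 40% | 1 to 2 | 20% to 40% |
| 4 | 4/5 = 80% | 2 to 4 | 40% to 80% |
| 6 | 6/5 = 120% | 3 to 5 | 60% to 100% |

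The SAP figure is at best right and otherwise too high.

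**Step 3: denominator (m = 1, so E = a).** Here a/5 = (a/k) × (k/5), so the share of those exposed is scaled down by k/5.

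| Exposed k | Affected a | SAP figure a/5 | Share of exposed a/k |
|---|---|---|---|
| 5 | 1 | 20% | 20% |
| 4 | 1 | 20% | 25% |
| 4 | 2 | 40% | 50% |
| 3 | 1 | 20% | 33.3% |

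If five were enrolled in each row, a/5 is still a correct share of those enrolled. It is not the share of those exposed. If only three were ever enrolled, the last row's 20% is a share of neither group.

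**Step 4: both together.** With four exposed and one participant having two events, the SAP figure is 2/5 = 40% against 1/4 = 25%. The two errors pull in opposite directions but rarely cancel. For k below 5, E/5 = a/k requires 5a = Ek. As 5 shares no factor with k, a must be 0 or k, so the figures agree only with no events, or with exactly five events and every exposed participant affected.

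**Step 5: participants with at least one event over those exposed.** One person with two events, five exposed: 1/5 = 20% (SAP 40%). Three people with six events, five exposed: 3/5 = 60% (SAP 120%). One person with one event, four exposed: 1/4 = 25% (SAP 20%).

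**The case against.** The best defence is that the sentence probably means something simple. The pain scale is the only tolerance measure the protocol calls a score, and the interview is described as qualitative. One pain rating per person, classed yes or no, gives at most one event each. The schedule's single-question survey may be that same rating. The figures above 100% therefore need the interview, or a repeated rating, to generate separately counted events, and no text says that it does. This stands: those figures show what the rule permits and are not a forecast.

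On the denominator, the SAP speaks of the whole group, and its 5 may only restate the planned size. The MFE follows the colonoscopy in the same session, so there is little time for loss before exposure. This also largely stands, but the SAP writes 5, and the protocol allows for fewer.

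Three stronger readings are tempting, and the documents do not support them:

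- *The figure is not a share of participants at all unless all five receive the MFE.* This goes too far. With five enrolled and at most one event each, it is a valid share of those enrolled.
- *The plan fails to define a non-tolerability event.* The supplied text has no definition, but Appendices B (pain scale) and C (interview) were not supplied and may contain one.
- *The primary-outcome sentence needs the same rewrite.* It already counts participants, so the mismatch of units does not arise there. Reporting success over those enrolled is a defensible choice.

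**Conclusion.** The point holds as a minor clarification. As written, the ratio mixes units and fixes its base at 5. It is sure to be the share of MFE-exposed participants who did not tolerate the device only when all five are exposed and no one has more than one event. That is the likely outcome, and the effect is then nil. Otherwise the figure can be too high (up to 120% against 60% in the case worked, if two events per person are possible) or too low (20% against 25% with four exposed, 20% against 33.3% with three). These sizes rest on assumed event counts and exposure numbers. The analysis is descriptive throughout, and adverse events are collected separately (Protocol 3.3.0.1), so neither the conduct of the study nor its safety reporting is affected.

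**What to change.** Replace the tolerability sentence in the SAP with:

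> Tolerability: number and percentage of participants with at least one non-tolerability event, out of participants in whom MFE insertion was attempted; total events listed separately, with the number enrolled and number attempted shown.

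Showing both numbers lets a reader recover the share of those enrolled as well.

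As an accompanying clarification, made before any data are seen, name the instrument and the rating or answer that counts as an event, or cite the appendix that does so. No cut-off is proposed here.

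The cost is one rewritten sentence and one extra reported line for the number attempted. The SAP already plans to report event counts as well as percentages, so listing events adds almost nothing. Design, sample size and study procedures do not change.
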